#### 9.2.4.3 Procedure for Reporting a Serious Adverse Event

For any SAE occurring during the clinical study, regardless of whether or not related to the study drug and/or procedure, the Investigator must:

1. Take prompt and appropriate medical action, if necessary. The safety of the subject is the first priority.
2. Ensure that the event is evaluated as an SAE. Immediately notify (**within 24 hours of receipt of the event**) the Syneos Health Safety and Pharmacovigilance group of an SAE report, by email or fax:

**[contact]**

**Safety email: [[contact]](mailto:[contact])**

Note: Immediate SAE reporting is required by the Investigator if it occurs during the clinical study or within 12 weeks ( $\pm$  5 days) of receiving the last dose of study drug, whether or not the event is considered to be related to the investigational product.

---

The demographics, medical history, drugs/therapies, and medical and surgical procedures forms must also be available for review in the eCRF, at that time.

3. Send any relevant information or anonymized medical records (e.g., laboratory test results) to the Syneos Health Safety and Pharmacovigilance group (see contact details above), within 24 hours of receipt of this relevant information.
4. Monitor and record the progress of the event until it resolves or reaches a stable condition, with or without sequelae. For all additional follow-up evaluations, complete an updated SAE report **within 24 hours** of receipt of the updated information.
5. Obtain and maintain in the subject files all pertinent medical records, information, and medical judgments from colleagues who participate in the treatment and follow-up of the subject. If necessary, contact the subject's personal physician or hospital staff to obtain further details.
6. When the outcome of the event is known, complete an updated SAE report, if appropriate.
7. Prompt notification of SAEs by the Investigator is essential so that legal obligations and ethical responsibilities toward the safety of subjects are met. The Sponsor has a legal responsibility to notify both the local regulatory authority and other regulatory agencies about the safety of a product under clinical investigation. The Sponsor or its delegate (i.e., the CRO) will comply with country-specific regulatory requirements relating to safety reporting to regulatory authorities, Institutional Review Board (IRB)/Independent Ethics Committee (IEC) and Investigators. Investigator safety reports are prepared for SUSARs according to local regulatory requirements, and are forwarded to Investigators as necessary.

An Investigator who receives an Investigator safety report describing an SAE(s) or other specific safety information (e.g., summary or listing of SAEs) from the Sponsor or its delegate (i.e., the CRO) will file it accordingly (i.e., within the Trial Master File [TMF]), and will notify the IRB/IEC, if appropriate according to local requirements.

8. Comply with the applicable regulatory requirement(s) related to the reporting of SAEs to the IRB/IEC.

#### 9.2.4.4 Procedure for Reporting Pregnancies

Any pregnancy occurring during clinical studies where the fetus could have been exposed to the study drug must be monitored until its outcome, in order to ensure the complete collection of safety data. If a subject becomes pregnant, the investigator must:

1. Withdraw the subject from the clinical study. The subject must not receive any further study drug.
2. Complete as fully as possible the Pregnancy Surveillance Form – Part I: History and Start of Pregnancy. Send by email or fax along with the exit form within 24 hours of receipt of the

---

information, to the Syneos Health Safety and Pharmacovigilance group. Refer to [Section 9.2.4.3](#).

Note: Immediate pregnancy reporting is required by the Investigator if it occurs during the clinical study or within 12 weeks ( $\pm$  5 days) of receiving the last dose of study drug, whether or not the event is considered to be related to the investigational product.

3. Monitor and record the progress of the pregnancy until its outcome. Contact the subject's regular physician (general practitioner or gynecologist) or hospital staff to obtain further details, and ask for regular follow-up information.
4. Provide tri-monthly updates until the final outcome of the pregnancy, by completing the Pregnancy Surveillance Form – Part II: Course and Outcome of Pregnancy. For all additional follow-up evaluations, send the form by email or fax to the Syneos Health Safety and Pharmacovigilance group within 24 hours of receipt of the information. If the subject can no longer be reached (i.e., lost to follow-up), documentation of the non-response/contact with 2 phone calls and a letter (certified with return receipt) is required.
5. At the outcome of the pregnancy, complete as fully as possible the Pregnancy Surveillance Form – Part II: Course and Outcome of Pregnancy. Print and send the form by email or fax to the Syneos Health Safety and Pharmacovigilance group within 24 hours of receipt of the information.
6. If the pregnancy leads to an abortion (i.e., voluntary abortion, spontaneous abortion, or therapeutic abortion), *in utero* death, or congenital anomaly, follow the procedure for declaration of/reporting an SAE (see [Section 9.2.4.3](#)).

#### **9.2.4.5 Unexpected Adverse Reactions**

##### **Unexpected Adverse Reaction Definition**

An unexpected adverse reaction is any untoward and unintended response that is related to the administration of the study drug at any dose, the nature or severity of which is not consistent with the applicable product information (e.g., reference safety information in the IB for MAL 16.8% cream, study protocol).

The Sponsor or its delegate (i.e., Syneos Health) will comply with country-specific regulatory requirements relating to safety reporting to regulatory authorities, IRB/IEC, and Investigators. Investigator safety reports are prepared for SUSARs according to local regulatory requirements and sponsor policy, and are forwarded to Investigators as necessary.

An Investigator who receives an Investigator safety report describing an SAE(s) or other specific safety information (e.g., summary or listing of SAEs) from the Sponsor or its delegate (i.e., Syneos Health) will file it accordingly (i.e., with the TMF), and will notify the IRB/IEC, if appropriate, according to local requirements.

#### **9.2.5 Clinical Laboratory Evaluation**

---

The hematology laboratory analyses, clinical chemistry laboratory analyses, and urinalyses will be performed at a central laboratory. Reference ranges will be supplied by the central laboratory and used by the Investigator to assess the laboratory data for clinical significance and pathological changes.

The Investigator or medically-qualified sub-investigator must review and evaluate laboratory values for each subject in a timely manner. Study centers should refer to the current version of the laboratory manual for laboratory values outside of normal limits. For each out-of-range laboratory result, the Investigator or designee will evaluate whether he/she considers it to be clinically significant (CS), defined as meeting at least 1 of the following conditions:

- The abnormality suggests a disease and/or organ toxicity, or
- The abnormality is of a degree that requires additional active management, e.g., discontinuation of the drug, close observation, more frequent follow-up assessments, or further diagnostic investigation.

If the Investigator observes a CS laboratory result, the test will be repeated as soon as possible and the subject will be monitored until the value returns to normal and/or an adequate explanation for the abnormality is found.

Investigators will also be allowed to repeat specific laboratory test(s) or procedure(s) where he/she suspects an inaccuracy or false result, and which may impact the safety of the subject or the interpretation of the study results; only after discussion with the medical monitor.

All CS out-of-range laboratory values at the screening visit will be recorded (report a diagnosis rather than the laboratory value, whenever possible). All CS out-of-range laboratory values after the screening visit are to be reported as an AE if this abnormality was not present at the screening visit or is assessed as having worsened since the screening visit (i.e., changed significantly from the screening visit). Whenever possible, the Investigator should provide a diagnosis of an AE when reporting the abnormal laboratory value.

Subjects should be reminded to be well hydrated before all visits for phlebotomy purposes. Subjects should fast for at least 8 hours before the visits when blood chemistry testing is planned, except for the screening visit. The screening visit laboratory values must be available before the baseline visit. Laboratory testing conducted in a nonfasting state will not be a protocol deviation.

Total blood volumes to be drawn at each visit are provided in the clinical laboratory manual. Additional samples may be required if medically indicated (e.g., at unscheduled visits for safety reasons, when an abnormal laboratory value is observed and requires a re-test).

See [Section 9.2.6](#) for details about pregnancy testing

The following laboratory safety tests will be performed as specified in [Section 8.1.2](#):

#### **9.2.5.1 Hematology**

---

Hemoglobin, hematocrit, white blood cell count (with differential including eosinophils), red blood cell count, platelet count, mean cell volume, and INR.

### 9.2.5.2 Clinical Chemistry

Creatinine, AST, ALT, gamma glutamyltransferase, alkaline phosphatase, lactate dehydrogenase, total bilirubin, direct bilirubin, albumin, total protein, uric acid, sodium, potassium, calcium, chloride, glucose, urea, total cholesterol, triglycerides, low-density lipoprotein, high-density lipoprotein (HDL), creatinine phosphokinase (CPK). Creatinine phosphokinase isoenzyme test will be performed only if CPK is elevated to  $>2.5 \times \text{ULN}$ . The Investigator should also contact the medical monitor in such situations.

For postmenopausal subjects (i.e., no menses for 12 consecutive months), postmenopausal status will be confirmed with a high follicle-stimulating hormone level in the postmenopausal range.

### 9.2.5.3 Urinalysis

pH, glucose, ketones, blood, protein, leukocytes, nitrites, bilirubin, urobilinogen, and specific gravity

### 9.2.6 Pregnancy Testing

All women of childbearing potential will have a urine pregnancy test at Visit 1 and UPTs at subsequent visits at Visits 2, 4, and 6 according to [Section 8.1.2](#). Pregnancy test results must be available prior to the administration of the study drug.

Subjects with a positive serum pregnancy test result at Screening must not be enrolled.

Urine pregnancy tests with a sensitivity  $< 25 \text{ IU/L}$  will be provided to the study centers for use in the study.

Urine pregnancy tests will be performed at the study centers, and all other samples will be sent to the central laboratory for analysis.

If the result of a UPT is positive, it must be confirmed with a serum pregnancy test, and no study drug should be administered pending the serum pregnancy test result. Subjects with a positive serum pregnancy test result during the study must discontinue treatment and be withdrawn from the study.

### 9.2.7 Vital Signs

Vital signs will be evaluated at the screening visit and at the final visit according to [Section 8.1.2](#) before blood sampling. Vital signs will include pulse rate, systolic and diastolic blood pressure (after the subject has been sitting for at least 15 minutes), and body temperature. All abnormal values at the screening visit, identified as CS by the Investigator will be recorded. Any CS changes from the screening visit will be recorded as an AE.

---

### 9.2.8 Physical Examination

A complete physical examination should be performed at the screening and final visits, according to [Section 8.1.2](#). A complete physical examination will include assessments of the head, ears, eyes, nose, throat, neck (including thyroid), skin/integumentary system, cardiovascular system, respiratory system, gastrointestinal system, musculoskeletal system, lymph nodes, and nervous system.

Investigators should assess all abnormal findings for clinical significance. All CS abnormal findings at the screening visit will be recorded in the medical history form. Any CS changes from the screening visit will be recorded as an AE.

### 9.2.9 Electrocardiogram

A 12-lead ECG will be performed and read centrally according to visits specified in [Section 8.1.2](#) using the ECG machine provided. Electrocardiograms for each subject should be obtained using the same electrocardiograph machine whenever possible. Electrocardiograms will be performed in the supine position at the time points described in the schedule of assessments and before any scheduled vital sign measurements and blood draws. Subjects should be monitored for potentially CS ECG results (refer to the current version of the central laboratory manual). Tests with abnormal results that are deemed CS should be repeated to ensure reproducibility of the abnormality. Any abnormalities considered to be CS by the Investigator are to be recorded as AEs and discussed with the medical monitor, as needed.

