**Table 9: Scale for Clinical Assessment of Subject's Skin Aspect**

|           |   |  |
|-----------|---|--|
| Excellent | 3 | No scarring, atrophy or induration, and no or slight occurrence of redness or change in pigmentation compared to adjacent skin |
| Good      | 2 | No scarring, atrophy or induration, but moderate redness or change in pigmentation compared to adjacent skin                   |
| Fair      | 1 | Slight to moderate occurrence of scarring, atrophy or induration   |
| Poor      | 0 | Extensive occurrence of scarring, atrophy or induration  |

In the event of the score of 2 or less for the clinical assessment of subject's skin aspect, it will be recorded as an AE in the eCRF.

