10.7.6 Clinical Laboratory Tests Analysis

Descriptive statistics (n, mean, standard deviation, median, first and third quartile, min and max) by treatment group and overall will be presented for blood chemistry, hematology and quantitative urinalysis parameters at baseline and visit 6/ET and for their change from baseline to visit 6/ET.

Statistical Analysis Plan

For summary purposes, laboratory values that are listed as above or below particular thresholds will be numerically imputed as above or below that threshold, respectively, by the minimum measured amount for that parameter. For example, if a parameter is measured to two decimal places, and has a result of "> 5" then, for summary purposes, the value of 5.01 will be used.

Number and percentage (n, %) of subjects for each response category of qualitative urinalysis parameter will be presented by treatment group and overall at baseline and visit 6/ET.

Number and percentage (n, %) of subjects with laboratory test values below, within and above the laboratory reference ranges will be summarized by treatment group and overall at baseline and visit 6/ET.

Number and percentage (n, %) of subjects with Clinically Significant Abnormal Values (as identified by the Investigator) and with Potentially Clinically Significant Values (see section 13.3) will be summarized by treatment group and overall at baseline and visit 6/ET.

Shift tables from baseline to visit 6/ET describing shifts to abnormality will be provided as well. Only subjects with a baseline result and a result at visit 6/ET for the parameter will be considered.

A listing of all clinical laboratory test will be provided.

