10.7.7 Electrocardiograms Analysis

The number and percentage (n, %) of subjects who have Investigator's interpretation of ECG 'Normal', 'Abnormal/Not Clinically Significant' and 'Abnormal/Clinically Significant' will be presented by treatment group and overall at baseline and visit 6/ET.

A listing of Investigator's interpretation of ECG results and a listing of ERT ECG results will be provided.

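### Of the four assessments made at both screening and Visit 6, only ECG has an adverse-event rule with no new-or-worsened condition, and its summary table cannot separate new from persisting abnormalities

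*Protocol*

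**What the plan says.** **Adverse-event rules.** Protocol 9.2.9 states: "Any abnormalities considered to be CS by the Investigator are to be recorded as AEs". SAP 6.2.8 repeats the rule. Neither compares with the screening ECG or says where a finding already present at screening is to be recorded.

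The three companion assessments are worded differently. For vital signs, protocol 9.2.7 says "Any CS changes from the screening visit will be recorded as an AE". Protocol 9.2.8 has the same sentence for physical examination and sends CS screening findings to the medical history form. For laboratory values, protocol 9.2.5 makes a CS result an event only "if this abnormality was not present at the screening visit or is assessed as having worsened since the screening visit".

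**Planned summaries.** Under SAP 10.7.7 the investigator's ECG reading is classed as normal, abnormal/not CS or abnormal/CS, and the counts "will be presented by treatment group and overall at baseline and visit 6/ET". Two ECG listings are also planned, one of the investigator's interpretation and one of the central results. Protocol 10.1.4.6 likewise asks for counts at each visit. For laboratory tests, SAP 10.7.6 goes further: "Shift tables from baseline to visit 6/ET describing shifts to abnormality will be provided as well".

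**The concern.** A CS arrhythmia or conduction defect that predates treatment meets the ECG rule at screening and meets it again, unchanged, at Visit 6. Nothing in the rule tells the investigator that the second sighting is not a new event. The other three assessments carry that instruction.

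What is at stake is how cleanly safety can be read. The treatment-emergent tables may pick up cardiac findings that existed before the first application. The ECG summary, which would be the natural place to check, shows only how many subjects were abnormal at each visit and not whether they were the same subjects.

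**Working it through.** The plan states no figure on this point, so there is none to reproduce. The check compares the text and adds a small illustration.

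**1. Rules and displays side by side**

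| Assessment | AE rule tied to screening? | Planned display of change |
|---|---|---|
| Laboratory | Yes, new or worse (protocol 9.2.5, SAP 6.2.5) | Change from baseline and shift tables (SAP 10.7.6) |
| Vital signs | Yes, change (protocol 9.2.7, SAP 6.2.6) | Change from baseline (SAP 10.7.5); flagging criteria that require a change (SAP 13.2) |
| Physical examination | Yes, change (protocol 9.2.8, SAP 6.2.7) | None; counts per visit (SAP 10.7.4) |
| ECG | No (protocol 9.2.9, SAP 6.2.8) | None; counts per visit (SAP 10.7.7) |

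ECG is the only row with neither a conditional rule nor a display of change. Protocol 10.1.4.3 also states that abnormal baseline laboratory values are not treatment-emergent. ECG has no matching statement.

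**2. Can a stable abnormality become treatment-emergent?**

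Inputs: adverse events are collected from consent (footnote e to protocol Table 3). The form takes the date the event first occurred (protocol 9.2.4, documentation of adverse events). SAP 10.7.3 counts an event as treatment-emergent if it began or worsened on or after the date of first application, and lists pre-treatment events separately. SAP 10.1.2 gives the date imputation rules.

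- Recorded at screening with its true onset date and unchanged later: pre-treatment, so not counted.
- Recorded again at Visit 6 with the Visit 6 date: counted.
- Start date wholly missing: imputed to the first treatment date, so counted.
- Only the year known, and it is the year of first treatment, or only month and year known, and they match first treatment: imputed to the first treatment date, so counted.
- Partial date from an earlier year or month: imputed to the start of that period, so not counted.

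The route exists, but it needs a repeat recording or an incomplete date.

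**3. What counts per visit can show**

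Let n be the arm size, B the number with a CS ECG at baseline and V the number at Visit 6, with every subject assessed at both. If only B and V are known, the number of new CS ECGs lies between max(0, V − B) and min(V, n − B). The documents give no CS ECG rate, so the rates below are assumed, equal at both visits, and rounded to whole subjects.

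| Assumed rate | MAL, n = 380: B = V | New CS | Vehicle, n = 190: B = V | New CS |
|---|---|---|---|---|
| 1% | 4 | 0 to 4 | 2 | 0 to 2 |
| 2% | 8 | 0 to 8 | 4 | 0 to 4 |
| 5% | 19 | 0 to 19 | 10 | 0 to 10 |

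With equal counts at the two visits, the table fits anything from no new abnormality to every Visit 6 abnormality being new.

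**4. Visibility in the common-event table**

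SAP 10.7.3 tabulates treatment-emergent events occurring in more than 1% of the safety population. If all 570 planned subjects are treated, 5/570 = 0.88% falls short and 6/570 = 1.05% qualifies. The six would have to share a preferred term. This shows where the threshold lies; it does not estimate how many such events will occur.

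**The case against.** Three stronger readings are tempting, and the documents support none of them.

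- **That ECG is the only finding recorded as an event without a screening comparison.** It is not. The protocol's skin-aspect scale creates an event "In the event of the score of 2 or less for the clinical assessment of subject's skin aspect", and pain needing an intervention is also recorded as an event (protocol 9.2.1). Neither refers to screening. Both, however, are assessed only once treatment has begun, so there is no screening value to compare. Among the four assessments with a screening value, ECG does stand alone.
- **That a stable abnormality will be counted as treatment-emergent.** Several provisions point the other way: collection starts at consent, the date asked for is that of first occurrence, a separate event is called for when severity changes, and pre-treatment events are listed apart. A finding correctly recorded at screening stays out of the tables unless it worsens. The date imputation rule applies to every event and is not an ECG defect.
- **That new ECG abnormalities cannot be identified.** They can, subject by subject, from the listings in SAP 10.7.7. Only the summary table hides them.

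It can also be said that physical examination has no shift table either, that exclusion criteria 6 and 13 may remove some subjects with serious cardiac disease, and that the maximal-use study reported no clinically significant ECG changes (protocol 6.2.2), so no known signal would be masked. These points are fair and keep the issue small. The physical-examination parallel is incomplete, because its event rule already requires change.

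**Conclusion.** The inconsistency is real and minor. ECG is the one assessment made at both screening and Visit 6 whose event rule omits the new-or-worsened condition, and its summary cannot distinguish new from persisting abnormalities.

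Entry of long-standing findings into the treatment-emergent tables is possible but depends on a repeat recording at Visit 6 or an incomplete start date. Its size cannot be given from the documents. The 1% to 5% rates used above are assumptions, and the ranges they produce describe the table's ambiguity, not expected counts. The efficacy analysis is untouched. No bias between arms is shown either: the same recording rule applies to both arms under blinding.

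This is a low-cost improvement to safety reporting and does not call any planned conclusion into question.

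**What to change.** 1. In protocol 9.2.9 and SAP 6.2.8, align the ECG sentence with the other three assessments: CS findings on the screening ECG are recorded as baseline findings or medical history, and a later CS finding is an adverse event only if it is new or has worsened since screening.
2. In SAP 10.7.7, add a shift table by arm, baseline by Visit 6/ET, with categories normal, abnormal/not CS, abnormal/CS and missing. Keep the existing counts, because protocol 10.1.4.6 calls for a display at each visit. The missing category retains subjects with only one ECG, whom the laboratory shift table drops.

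The cost is one sentence in each document and one extra table from data already collected. If the protocol wording can no longer be changed, the shift table alone still separates new from persisting abnormalities in the summary, though it does not alter what has been recorded as an event.
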